EDC	electronic data capture
EHDN	European Huntington's Disease Network
ET	early termination
FDA	Food and Drug Administration
GCP	Good Clinical Practice
HD	Huntington's disease
HED	human equivalent dose
HTT , HTT	Huntingtin gene or huntingtin protein
IB	Investigator's Brochure
ICF	informed consent form
ICH	International Conference on Harmonisation
INN	International Nonproprietary Name

Abbreviation	Definition
IRB	Institutional Review Board
IT	intrathecal
IUD	intrauterine device
IUS	intrauterine hormone-releasing system
IXRS	interactive voice/web response system
MedDRA	Medical Dictionary for Regulatory Activities
mHTT , mHTT	mutant huntingtin gene or protein
MMRM	mixed model for repeated measures
MRI	magnetic resonance imaging
mRNA	messenger ribonucleic acid
NFL	neurofilament light
OLE	Open-label extension
PBA-HD	Problem Behaviors Assessment for HD
PBA-s	Short Problem Behaviors Assessment
PD	Pharmacodynamic(s)
PK	Pharmacokinetic(s)
PS	phosphorothioate
PT	prothrombin time
QTc	QT interval corrected for heart rate
RNA	ribonucleic acid
RSI	reference safety information
SAE	serious adverse event
SDMT	Symbol Digit Modalities Test
SMC	Safety Monitoring Committee
SNP	single nucleotide polymorphism
SNP1	single nucleotide polymorphism rs362307
SOC	system organ class
SOP	Standard Operating Procedure
SUSAR	suspected unexpected serious adverse reaction
TEAE	treatment-emergent adverse event
TFC	Total Functional Capacity
t_{\max}	time of occurrence of C_{\max}
U	uracil
UHDRS	Unified Huntington's Disease Rating Scale
ULN	upper limit of normal
wtHTT	wild-type huntingtin

1 INTRODUCTION

WVE-120101 is intended as a disease-modifying agent for the treatment of patients with Huntington's disease (HD). It is a stereopure antisense oligonucleotide (ASO) intended to selectively target the mutant form of the *huntingtin* (*mHTT*) gene transcript at the uracil (U) variant of single nucleotide polymorphism (SNP) rs362307 (SNP1).

1.1 Disease Background

Huntington's disease is a rare, progressive neurological disease that results in motor, cognitive, and psychiatric disability and is invariably fatal¹. Because it is a genetic, hereditary disease, it can affect multiple family members across generations². Although cognitive and psychiatric symptoms may develop first, the clinical diagnosis of HD is usually based on the presence of chorea, one of the most visually prominent symptoms of this disease. Chorea is an abnormal involuntary movement disorder, which occurs in 90% of patients and is moderate to severe in approximately 70% of these patients. These physical symptoms can appear at any age, but typically appear between the ages of 30 and 50¹. A physical examination, sometimes combined with a neurological examination, can determine whether the onset of the disease has begun. Life expectancy after symptom onset is reduced to around 15 to 20 years^{1,2}. Prevalence in Europe, North America, and Australia is approximately 6 per 100,000³. In the United States alone, approximately 30,000 people have diagnosed HD^{4,5} and another 200,000 or more Americans carry the gene and are at risk of developing the disease⁵. Currently, no treatments exist that can cure, slow, or reverse the course of HD. Some of the symptoms of HD can be managed with medication and therapies such as antipsychotics and drugs that affect the dopamine pathways, which modulate the movement disorder².

Huntington's disease is caused by known mutations in a single gene, that are characterized by an expansion of a cytosine-adenine-guanine (CAG) triplet repeat in the *Huntingtin* (*HTT*) gene⁶. Wild-type HTT (wtHTT) protein is critical for neuronal development⁷. Although the purpose of wtHTT in adults is not completely understood, some studies have shown that it may play an important role in neuronal functions⁷⁻¹⁰. However, expansion in the CAG triplet repeat in the *HTT* gene results in production of the mHTT protein. Accumulation of this protein leads to progressive loss of neurons in the brain². In nonclinical studies, lowering the level of mHTT protein as measured in the cerebrospinal fluid (CSF) has been demonstrated to be therapeutic^{11,12}. Therefore, a drug that can silence the *mHTT* gene transcript, while leaving the wild-type allele intact, may be able to slow down, stop, or even reverse the course of HD¹³.

1.2 Investigational Product WVE-120101

WVE-120101 is an oligonucleotide, a type of nucleic acid that includes innovative drugs that are assembled from chemically modified, short-length ribonucleic acid (RNA) or deoxyribonucleic acid (DNA) strands. The potential therapeutic uses of oligonucleotides include modulating the function of target RNAs to affect the production of disease-associated proteins. The mechanism of action used by many oligonucleotides, including ASOs, is to promote degradation of the target RNA. Phosphorothioate (PS) modification was one of the earliest and remains one of the most

common backbone modifications used in oligonucleotide synthesis. These modifications improve the stability, biodistribution, and cellular uptake of oligonucleotides. The use of PS modification in oligonucleotide synthesis creates a chiral center at the phosphorus of each PS, which has either an “Sp” or “Rp” configuration at random. A conventional, fully PS-modified oligonucleotide (20 nucleotides in length, 19 PS modifications) is a mixture of over 500,000 stereoisomers (2^{19}), each having the same nucleotide sequence but differing in the stereochemistry along its backbone, resulting in heterogeneous and uncontrolled pharmacological properties.

The Sponsor has developed PRISM™, a proprietary technology that enables the synthesis of PS-modified nucleic acid therapeutics in which stereochemistry at each PS position is precisely controlled. This degree of control enables rational design and synthesis of optimized, or stereopure, oligonucleotides with improved pharmacological and toxicological properties as compared to stereorandom molecules.

WVE-120101 specifically targets the mHTT messenger ribonucleic acid (mRNA) transcript, at the U variant of SNP1. A SNP is a single variation in the DNA that can be associated with a mutated gene. One of the most frequent SNPs in the *mHTT* gene is SNP1, which has been shown to be present in approximately 50% of patients with HD¹³⁻¹⁶.

1.3 Nonclinical Data

The nonclinical program evaluating WVE-120101 encompasses in vitro studies of primary and secondary pharmacology, in vitro and in vivo genetic toxicology, and in vivo safety pharmacology and toxicity studies.

In vitro pharmacology studies confirm that WVE-120101 demonstrates selective knockdown of the mHTT messenger ribonucleic acid (mRNA) and protein through cleavage of the mRNA transcript of the mutant allele with the targeted single nucleotide polymorphism (SNP) rs362307 (SNP1) versus the wild type allele. This selective knockdown results in greater reduction of the mHTT protein over wild type huntingtin (wtHTT) protein produced by this ribonucleic acid (RNA) and, thus, limits the unintended, potentially deleterious effects of decreasing wtHTT⁷⁻¹⁰. In vivo tissue distribution studies in animals demonstrate that, upon intrathecal (IT) administration, WVE-120101 distributes to the brain, the intended target tissue where it may be able to produce sustained and effective target suppression of mtHTT. However, in the absence of an animal model recapitulating the mutation observed in this subpopulation of HD patients, no in vivo data are available regarding the concentration required to reduce the level of mHTT in vivo or the potential duration of knockdown. The optimal dose and dosing frequency for efficacy in humans will be explored during clinical development.

In vitro, WVE-120101 is highly protein-bound in rat, monkey, and human plasma (>99%). Following single or multiple monthly intrathecal (IT) administrations of WVE-120101 in rats and monkeys, dose dependent increases were observed in plasma, central nervous system (CNS), and systemic tissues (kidney, liver, and spleen). Systemic accumulation of WVE-120101 after repeated dosing was minimal. No in vitro cytochrome P450 (CYP) inhibition or induction was observed at clinically relevant concentrations of WVE-120101.

In single and repeat-dose IT studies in rats and monkeys, transient, dose-dependent limb dysfunction was observed. In rats findings were observed at dose levels of 0.1 mg (human equivalent dose [HED] 56 mg) in a single-dose study and 0.05 mg (HED 28 mg) and above in repeat doses. These findings resolved within 72 hours. In monkeys, findings were observed at doses up to 6 mg (HED 67.2 mg). Over the course of 9 months in a chronic toxicity study in monkeys, affected animals at doses ≤ 2 mg experienced only 1 or 2 instances of limb dysfunction at sporadic time points. In monkeys, only the lower hind limbs were affected and findings were completely resolved within 48 hours post-dose. Due to their transience, lack of correlating histopathology, and lack of effect on the ability of animals to eat or ambulate, the findings were considered non-adverse.

Microscopic CNS findings were observed in both rats and monkeys after IT administration of WVE-120101. In rats, after 3 months of repeat IT dosing, cellular infiltrates, minimal to mild non-adverse spinal nerve root degeneration, and gliosis were observed. The findings were dose- and/or dose-concentration dependent, with minimal effects observed at 0.05 mg (dose concentration 2 mg/mL). In monkeys, after 3 to 9 months of repeat IT dosing, minimal to mild (3-month study) or minimal to moderate (9-month study) mononuclear cell infiltrates were observed at all doses evaluated. These findings were considered manifestations of the injection procedure and a general response to the immune-stimulating properties of the oligonucleotide^{17,18} and were considered non-adverse.

WVE-120101 demonstrated minimal potential for class effects associated with phosphorothioate oligonucleotides, such as systemic pro-inflammatory effects, activated partial thromboplastin time (aPTT) prolongation, hepatotoxicity, and nephrotoxicity^{18,19}. In addition, WVE-120101 was not associated with any other toxicities, including mutagenicity or effects on cardiovascular or respiratory function, and WVE-120101 exhibited minimal potential for off-target effects via bioinformatic analysis of the human genome.

In an *in vivo* genotoxicity study in rats, a statistically significant but non-dose-related increase in micronucleated polychromatic erythrocytes was observed in rats. This increase was not considered biologically meaningful, since the values were within the historical control range for the test facility and anti-kinetochore staining demonstrated that the findings were not the result of an aneugenic mechanism. Moreover, because WVE-120101 was negative in an *in vitro* panel of genotoxicity studies; there were no histological findings in long-term animal studies suggestive of effects on dividing cells; and because oligonucleotides are not known to carry a genotoxic risk; WVE-120101 is unlikely to induce genotoxic effects under the proposed conditions of use.

Based on the results of the nonclinical studies, the risk/benefit for further investigation of WVE-120101 as a disease-modifying agent for the treatment of patients with HD is acceptable. Further details on the nonclinical experience with WVE-120101 can be found in the current version of the Investigator's Brochure (IB).

1.4 Clinical Experience

WVE-120101 is currently being evaluated in a Phase 1b/2a multicenter, randomized, double-blind, placebo-controlled study to evaluate the safety, tolerability, pharmacokinetics (PK), and

pharmacodynamics (PD) of single and multiple doses of IT WVE-120101 in adult patients with early manifest HD who carry a targeted single SNP, SNP1 (WVE-HDSNP1-001).

In the Phase 1b/2a study, as of the last data cutoff at single doses up to 16 mg (20 March 2020) and multiple doses up to 4 mg (02 March 2020), no stopping criteria have been observed. No related SAEs or related TEAEs associated with the HLTG *Spinal Cord and Nerve Root Disorders* have been reported. No clinically meaningful trends in hematology, coagulation, or chemistry values followed dosing. Final data are not yet available from this study. An independent Safety Monitoring Committee (SMC) will continue to review safety data from study WVE-HDSNP1-001 on an ongoing basis. The SMC will also review data for this OLE study in conjunction to the data from the Phase 1b/2a study to inform decisions in dose escalation and continuation of multiple dosing. If any stopping rules are met in the Phase 1b/2a study, or if the SMC decides to stop the Phase 1b/2a study for any other reason, those decisions will also apply to this study. More detailed information is provided in the Investigator's Brochure.

2 RATIONALE FOR THE STUDY

This open-label extension (OLE) study is being conducted to evaluate the safety, tolerability and clinical effects of monthly IT doses of WVE-120101 over 97 weeks. Patients must complete their Day 168 or 196 visit (depending upon dosing cohort and requirements in a given country) of the prior Phase 1b/2a clinical study (WVE-HDSNP1-001) to be eligible for screening for this extension study.

2.1 Rationale for the Doses, the Dosing Regimen, and Route of Administration

This is an open-label extension study for the Phase 1b/2a clinical study WVE-HDSNP1-001. The clinical starting dose in WVE-HDSNP1-001 was selected in consideration of the data from both single- and 13-week repeat-dose toxicology studies; an animal model possessing the SNP1 variant targeted by WVE-120101 was not available to the Sponsor. The clinical starting dose of 2 mg was based on the no-adverse-effect-level (NOEL) for transient limb dysfunction in monkeys, which is considered the most relevant species for the purposes of clinical assessment. The lack of findings in the monkey at a dose of 2 mg provides a 10-fold safety margin to the HED, on the basis of relative CSF volume. Subsequent doses are selected based on safety assessments from each cohort.

In the original OLE study protocol, patients who were in the 2 and 4 mg dose cohorts in the Phase 1b/2a study were enrolled into the 4 or 8 mg dose group in this study. Patients who were in the 8 and 16 mg dose cohorts in the Phase 1b/2a study were enrolled into the 8 or 16 mg dose groups, respectively in this study. As of this amendment, patients will receive 16 mg or a higher dose of WVE-120101 in this study. The maximum dose and frequency in this OLE study in a given country will not exceed the maximum dose and frequency described in the Phase 1b/2a protocol (WVE-HDSNP1-001) approved in that country. If a dose lower than the maximum dose described in the Phase 1b/2a study is chosen for multiple dosing based on the safety review of the Phase 1b/2a study data by the Dose Escalation Committee (DEC) and Safety Monitoring Committee (SMC), that dose will be used in this OLE study.

Based on the SMC and DEC review of Phase 1b/2a safety data, the highest tolerated dose level and/or a lower dose level may be selected for multiple dosing and further evaluation in the OLE. If one dose level is selected, all patients will be switched to receive treatment at that dose level. If more than one dose is selected, patients will be randomized 1:1 to the highest tolerated dose and one lower dose to be determined by the DEC in agreement with the SMC. The randomization will be stratified by cohort and use a fixed block size. These doses may be further revised based on emerging safety, PD, or clinical effects data in the Phase 1b/2a study. The maximum dose and frequency in this OLE study will not exceed the maximum dose and frequency described in the Phase 1b/2a protocol (WVE-HDSNP1-001) approved in each country. For more details on additional dose modifications refer to [Section 4.1](#).

At the time when the Phase 1b/2a study is completed, the dose and dose interval in this OLE study may be further adjusted. A final determination about the optimal dose and dose-frequency will be made on the basis of data from the WVE-HDSNP1-001 study. It is possible that patients will be up-titrated or down-titrated depending on the dose they were receiving at the time of that decision. Up- or down-titration of the dose will only occur at the cohort level, not on an individual patient level.

The follow-up period will continue to Week 101, 4 weeks after the last dose. Based on PK data from animal studies, the plasma half-life of WVE-120101 is less than 24 hours and the potential for accumulation is low. Clinical data from the ongoing WVE-HDSNP1-001 study show that adverse events tend to occur within the first week or two after dosing. A 4-week follow-up period after the last dose is therefore considered a sufficient period of time to observe potential adverse events.

3 STUDY OBJECTIVES

Primary Objective:

The primary objective of this study is to evaluate the safety and tolerability of long-term exposure to WVE-120101 in patients with early manifest HD.

Secondary Objectives:

The secondary objectives of this study are to evaluate the clinical and pharmacodynamic effects of WVE-120101 in patients with early manifest HD.

Exploratory Objectives:

The exploratory objectives are:

- To evaluate the PK of WVE 120101 in plasma
 - To evaluate WVE-120101 related excretion in urine
 - To evaluate the exposure of WVE-120101 in CSF
-

- To evaluate the effect of WVE-120101 on exploratory biomarkers

4 STUDY DESIGN

4.1 Study Design Overview

[figure not shown]
This is an OLE study to evaluate the safety, tolerability, PK, PD, and clinical effects of WVE-120101 in adult patients with early manifest HD who carry a targeted single nucleotide polymorphism, SNP1. The planned duration of this study is approximately 101 weeks. To participate in the study, patients must have completed their Day 168 or 196 (depending upon dosing cohort and requirements in a given country) of the parent Phase 1b/2a clinical study [WVE-HDSNP1-001](#).

Screening may last up to 4 weeks. Patients will be dosed on Day 1 with WVE-120101 administered via the IT route and stay in the clinic for monitoring through 4 hours postdose.

Patients will return to the clinic every 4 weeks for dosing visits and safety monitoring. Every 12 weeks, patients will undergo assessments of clinical effects. After the last dosing visit (Week 97), patients will return for 1 follow-up safety visit at Week 101.

A schematic of the overall study design and timing is provided in [Figure 1](#).

Figure 1 Schematic of Study Design

[figure not shown]
Dose Modifications

In the original OLE study protocol, patients who were in the 2 and 4 mg dose cohorts in the Phase 1b/2a study were enrolled into the 4 or 8 mg dose group in this study. Patients who were in the 8 and 16 mg dose cohorts in the Phase 1b/2a study were enrolled into the 8 or 16 mg dose groups, respectively in this study. As of this amendment, patients will receive 16 mg or a higher dose of WVE-120101 in this study ([Figure 2](#)). The maximum dose and frequency in this OLE study in a given country will not exceed the maximum dose and frequency described in the Phase 1b/2a protocol (WVE-HDSNP1-001) approved in that country. If a dose lower than the maximum dose described in the Phase 1b/2a study is chosen for multiple dosing based on the safety review of the Phase 1b/2a study data by the Dose Escalation Committee (DEC) and Safety Monitoring Committee (SMC), that dose will be used in this OLE study.

Based on the SMC and DEC review of Phase 1b/2a safety data, the highest tolerated dose level and/or a lower dose level may be selected for multiple dosing and further evaluation in the OLE. If one dose level is selected, all patients will be switched to receive treatment at that dose level. If more than one dose is selected, patients will be randomized 1:1 to the highest tolerated dose and one lower dose to be determined by the DEC in agreement with the SMC (Figure 2). The randomization will be stratified by cohort and use a fixed block size. These doses may be further revised based on emerging safety, PD, or clinical effects data in the Phase 1b/2a study. The maximum dose and frequency in this OLE study will not exceed the maximum dose and frequency described in the Phase 1b/2a protocol (WVE-HDSNP1-001) approved in each country.

Dose modification will occur at the next scheduled visit from the date of implementation of this amendment (Amendment 1.0). In addition to the assessments performed at every dosing visit, the Unified Huntington's Disease Rating Scale (UHDRS) and clinical laboratory evaluations should be performed at the visit when a dose is changed. Patients will not be asked to restart the treatment phase but will continue to receive doses as originally scheduled, every 4 weeks, at the new dose level.

Figure 2 Dose Modification Scheme

Abbreviations: DEC=Dose Escalation Committee; SMC=Safety Monitoring Committee

*Dose modification randomization. Applicable if 2 doses are studied.

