5.1 Inclusion Criteria

1. Patient has documented ability to understand the written study ICFs and has provided signed written informed consent prior to any study procedures.
2. Patient successfully completed their Day 168 or 196 visit (depending upon dosing cohort and requirements in a given country) of the Phase 1b/2a study with WVE-120101, [WVE-HDSNP1-001](#).
3. In the opinion of the Investigator, the patient is able to tolerate all study procedures, is willing to comply with all other protocol requirements, and tolerated study drug in the parent study.
4. Patient is willing to practice highly effective contraception for the duration of the study if patients or their partners are of childbearing potential. Non-childbearing potential and highly effective methods of contraception are defined in the protocol ([Section 5.2.1](#)).

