7 BLINDING AND RANDOMIZATION

This is an open-label study. If the DEC and SMC endorse multiple dosing at a dose higher than 16 mg in the Phase 1b/2a study, patients in this OLE study may be randomized to new dose levels pending Sponsor decision. The randomization scheme will be assigned by an interactive voice/web response system (IXRS), which will send notifications of the treatment assignment to the designated pharmacy personnel.

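### If two doses are randomised, one fixed block size in this open-label extension makes part of the allocation predictable to someone who sees whole strata (minor)

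*Combined protocol and SAP*

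**What the plan says.** The randomisation is conditional. Section 4.1 provides that, if more than one dose is selected, "patients will be randomized 1:1 to the highest tolerated dose and one lower dose", and the note to Figure 2 reads "Applicable if 2 doses are studied". Section 7 is looser still: "patients in this OLE study may be randomized to new dose levels pending Sponsor decision".

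The allocation rule is one sentence: "The randomization will be stratified by cohort and use a fixed block size". It appears in the Synopsis and in Sections 2.1, 4.1 and 4.1.2. Section 7 states "This is an open-label study" and, on the mechanism, "The randomization scheme will be assigned by an interactive voice/web response system (IXRS), which will send notifications of the treatment assignment", with the notice going to designated pharmacy staff.

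Patients already in the extension change dose at their next scheduled visit (Section 4.1), and most treatment visits have a window of one week either side (Table 1). Patients still rolling over must pass criteria that include judgement, for example Inclusion 3: "In the opinion of the Investigator, the patient is able to tolerate all study procedures". Screening may take up to four weeks, and one rescreening is allowed for a transient failure (Section 5).

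Safety results are presented by dose group (Section 10.4.2). The MMRM has dose-group and time-by-dose-group terms, but no dose-versus-dose contrast is named (Section 10.4.4).

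The plan does not state:
- the block size, or who may know it;
- the size of the strata or the number of sites;
- how many patients will be enrolled at the dose decision;
- whether enrolled patients are allocated together or one at a time.

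**The concern.** In a 1:1 list with one constant block size, the last assignments of a block follow from those before them. Open-label treatment makes the earlier ones visible, and the protocol tells every reader that the block size is constant. A person who can foresee the next dose could let it influence whether or when a patient enters. For an enrolled patient, it could influence where in the window the visit falls.

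The randomised split is the only dose comparison in the extension that parent cohort and calendar time do not confound. It is descriptive, but safety is the primary objective and is tabulated by dose group, so readers will compare the columns. If entry or order depended on the coming dose, the groups could differ in adverse-event risk for reasons other than dose.

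**Working it through.** The plan gives no predictability figure, so there is nothing to reproduce.

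**Inputs from the documents.** 1:1 allocation, fixed blocks, strata defined by cohort and not by site, about 50 patients (Section 5), and four named parent cohorts (2, 4, 8 and 16 mg).

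**Assumptions.** Block size 2, 4 or 6. Four or five strata of similar size: 50/4 = 12.5 or 50/5 = 10 patients each. 5, 10 or 20 sites, with patients spread at random.

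**1. Full view of a stratum, block size known.** For a block of 2b, the expected share of assignments that are certain is 1/(b+1). The best guess is the dose behind within the block, with ties at 50%. For a block of 4 the success rate is (1/2 + 2/3 + 2/3 + 1)/4 = 70.8%. Enumerating all balanced blocks gives:

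| Block size | Certain | Best guess correct |
|---|---|---|
| 2 | 1/2 = 50.0% | 75.0% |
| 4 | 1/3 = 33.3% | 70.8% |
| 6 | 1/4 = 25.0% | 68.3% |

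An incomplete last block lowers the certain share. In simulated strata of 10 it is 50%, 27% and 16%.

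**2. View of one site only.** Strata cross sites, so one site sees fragments of each block. Simulation with strata of 13, 13, 12 and 12, crediting the observer with knowledge of where blocks begin when counting certain assignments:

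| Sites | Certain (blocks 2 / 4 / 6) | Guess correct (blocks 2 / 4 / 6) |
|---|---|---|
| 5 | 9.6% / 1.3% / 0.2% | 53.6% / 53.5% / 53.4% |
| 10 | 4.7% / 0.3% / about 0% | 52.1% / 52.1% / 51.9% |
| 20 | 2.3% / 0.1% / about 0% | 51.0% / 51.0% / 51.0% |

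Five strata of 10 give guess rates within 0.3 points of these.

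**3. Upper bound on bias.** Suppose there are two equally common patient types whose adverse-event risks differ by 20 points (an assumption), and every guess is acted on. With guess accuracy p, the bias in the difference between doses is at most (2p − 1) × 20 points.
- Full view: (2 × 0.750 − 1) × 20 = 10.0 for blocks of 2; 8.3 for blocks of 4; 7.3 for blocks of 6.
- One site: from (2 × 0.510 − 1) × 20 = 0.4 to (2 × 0.536 − 1) × 20 = 1.4.

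For scale, with 25 patients per dose and event proportions near 50%, the 95% half-width of the difference is 1.96 × √(2 × 0.5 × 0.5/25) = 0.28, or 28 points.

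**4. Effect of varying block sizes, full view.** The certain share falls to about 10% with sizes 2 and 4 mixed, 6% to 7% with 4 and 6, and 3% with 2, 4 and 6. Guess accuracy with 2, 4 and 6 mixed stays at about 69%, so the bound is (2 × 0.69 − 1) × 20 = 7.6 points, no better than fixed blocks of 6.

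**5. Effect of a single run.** If all assignments for enrolled patients are drawn before any is released, none can be predicted from the others, whatever the block size.

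**The case against.** The strongest reply is that those who could steer cannot see, and those who might see do not decide entry. Eligibility is the investigator's decision. The list is central, strata are pooled across sites, and a one-site view is close to chance.

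The population is also closed. Its size is capped by completers of the parent study (Section 10.1) and patients are not replaced (Section 5.3.4), so nobody has a pool from which to pick patient types. Patients already enrolled have entered, so foreknowledge cannot decide that. The block size is not disclosed in the protocol, and the text is compatible with a single run for enrolled patients. Randomisation may never take place, and the dose comparison is descriptive. Varying blocks do not lower the bias bound.

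Nearly all of this stands, and it limits the size of the point. Three things remain. The plan announces a constant block size and does not say that its value is withheld from study staff. It places no limit on who sees cumulative assignments. And being compatible with a single run is not the same as requiring one.

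**Conclusion.** The point holds in a limited form and is minor. If two doses are selected, someone who sees all assignments in a stratum and knows or infers the block size can be certain of 50%, 33% or 25% of them (blocks of 2, 4 or 6). A single-site investigator guesses correctly about 51% to 54% of the time. The exposure lies mainly with people who have a trial-wide view, and it affects patients still to enter and visit order within the window. These figures rest on assumed block sizes, stratum sizes and site numbers.

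A reader might infer two stronger things that the documents do not support:
- *That anyone who sees assignments can work out the next dose.* Even with a full view and a known block size, at most half of the assignments are certain, and cohort strata under a central IXRS leave one site with little to go on.
- *That the primary safety result is biased by 7 to 10 points.* That range needs a trial-wide view, complete steering of entry and an assumed 20-point risk difference. The same formula gives 0.4 to 1.4 points for a single-site observer.

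It is plausible, but not stated, that most patients will already be enrolled at the dose decision.

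**What to change.** In the Synopsis and Sections 2.1, 4.1 and 4.1.2, replace the fixed-block clause with two rules:

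1. All patients enrolled at the dose decision are randomised 1:1 within cohort in one IXRS run, before any assignment is released.
2. Later entrants are randomised from a central IXRS list with varying block sizes not disclosed to sites or study staff, and only after eligibility has been locked in the IXRS.

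Rule 1 is the stronger part, because it removes prediction for the patients it covers. Rule 2 removes most certain predictions and prevents eligibility from being decided after the dose is known, but it does not materially lower best-guess accuracy.

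The cost is one sentence in four places and a list specification, with no extra patients or visits. A stratum may end one or two patients out of balance (at most 6/2 = 3 in the later-entrant list if blocks go up to 6). Bias from unblinded outcome rating is a separate matter that this change does not address.
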